6.3 INTERCURRENT EVENTS

This section is not applicable.

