In the MRD part, three multiple dose cohorts will be studied over a 24 week-period. After an initial active treatment period of 12 weeks (3 injections in 4 weekly intervals) patients will be followed up for an additional 12 weeks without further injections to study the durability of the treatment effect and to identify the need for additional standard treatment and the time to development of recurrence of any retinal fluid. This will help to guide injection frequency intervals in later studies.

The therapeutic benefit or specific adverse events (AE) in patients cannot always be anticipated during the trial setup. Later on, there may be new scientific knowledge about biomarkers and other factors contributing to diseases or the action of a drug. In order to be able to address future scientific questions, patients will be asked to voluntarily donate biospecimens for banking. If the patient agrees, banked samples may be used for future drug development projects, e.g. to identify patients that are more likely to benefit from a treatment or experience an AE, and thereby better match patients with therapies or to gain mechanistic understanding of drug effects and/or to identify genetic or other factors associated with response to therapy or the risk of adverse drug reactions.

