## **4.2 OTHER TREATMENTS, EMERGENCY PROCEDURES, RESTRICTIONS**

### **4.2.1 Restrictions**

#### **4.2.1.1 Restrictions regarding concomitant treatment**

SRD and MRD cohorts 1 & 2: As per judgement of the investigator, administration of local SoC treatment such as IVT or peribulbar injections, laser, or other surgical treatment is allowed in clinically significant worsening of the disease. After the end of treatment with trial medication (during Follow-up Period, starting at Visit 5), SoC therapy is at the discretion of the investigator. SoC therapy is, for the purpose of the present trial, considered a non-investigational medical treatment.

MRD cohort 3: For the study eye, no other treatment (IVT or otherwise) is allowed during the treatment and follow up periods of the trial unless rescue criteria are met (refer to [Section 5.2.2](#) for rescue treatment criteria), or as deemed medically appropriate during/after Visit 6. Medications listed under the exclusion criteria ([Section 3.3.3](#)) are restricted during the trial. SoC therapy is, for the purpose of the present trial, considered a non-investigational medical treatment.

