6.4 SUBJECT SETS ANALYSED

Enrolled set (ES):

This subject set includes all patients who were enrolled in the study regardless of whether they were treated or not. The ES is used for the disposition table / listing and the disclosure tables for enrolment.

Section 7.3 of the CTP:

Treated Set (TS)

The TS will consist of all patients who were treated with at least one dose of BI 836880.

Full Analysis Set (FAS; only MRD part)

The FAS will consist of all patients who were treated with at least one dose of BI 836880 and have baseline and on-treatment CSFT measurements for the study eye in the time interval from drug administration to week 12. It will be used for the analysis of CSFT (change and percent change) only.

Evaluable Responders' Set (ERS, MRD cohort 3 only):

The ERS will consist of all patients who completed three doses of BI 836880 and have SD-OCT measurements at Week 16 (Visit 6) and haven't received SoC or any prohibited medication through week 16.

Patients with iPDs related to efficacy assessments that are expected to majorly affect the validity of assessment of efficacy at week 16 will be excluded from ERS. These include for

e.g., lack of compliance (including missed treatments, treatment misallocation and treatment/OCT assessment outside window), missing data, SoC or any prohibited medication, improper assessment at reading center and deviation from inclusion/exclusion criteria.

Any dropouts or withdrawals prior to completion of three doses of BI 836880 will be considered as a criterion of exclusion from ERS. In addition, any dropouts or withdrawals after completion of three doses of BI 836880 will also be excluded from ERS, unless SD-OCT measurements are available for that patient at Week 16.

Pharmacokinetic parameter analysis set (PKS):

This set includes all subjects in the treated set (TS)

- who received at least one dose of the test product BI 836880 and
- who provide at least one PK endpoint that was not excluded due to a protocol deviation relevant to the evaluation of PK or due to PK non-evaluability. Thus, a subject will be included in the PKS, even if he contributes only one PK parameter value for one period to the statistical assessment.

Descriptive and model-based analyses of PK parameters will be based on the PKS.

Table 6.4: 1 Subject sets analyzed

| Class of endpoint | ES | TS | FAS | ERS | PKS |
|---|----|----|-----|-----|-----|
| Primary endpoints | | X | | | |

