7.5.2 Secondary objective analysis

Section 7.3.2 of the CTP:

In principle, all secondary endpoints specified in [Section 5.2.2](#) will be analyzed descriptively, based on the TS. The analysis of percent change from baseline in CSFT in the study eye at week 12 (Visit 5) will be done by dose, based on the FAS.

Descriptive statistics for absolute values as well as changes from baseline (percent changes and changes in CSFT and changes in BCVA (study eye)) will be provided by dose group/cohort and in total. Time profiles of mean (\pm SD) absolute values and mean (\pm SD) changes from baseline by cohort as well as individual time profiles (absolute values and changes from baseline) per treatment group/cohort will be provided. For percent changes of CSFT, median and minimum/maximum values will be shown instead.

For those endpoints related to adverse events refer to [Section 7.8.1](#).

Section 5.2.2 of the CTP:

Time to recurrence will be assessed in the MRD part, based on the TS, from last trial drug administration to occurrence of any of the following in the study eye, leading to the use of wAMD rescue medication as decided by the investigator:

- *Increase in CSFT $\geq 75 \mu\text{m}$ with a decrease in BCVA of ≥ 5 letters compared to Visit 5, OR*
- *Decrease in BCVA of > 5 letters compared to baseline (Visit 2), due to worsening wAMD activity,*
OR
- *Decrease in BCVA of ≥ 10 letters compared to the best prior BCVA, due to worsening wAMD activity*

From above criteria, if Visit 5 BCVA/CSFT assessment data is missing, BCVA/CSFT values available earlier than Visit 5 will be used. The last trial drug administration is strictly referring to the third injection, if a patient doesn't complete three injections, the patient will not be evaluated for time to recurrence endpoint and will be censored as per [Table 7.5.2:1](#). The details of censoring rules are listed in the [table](#) below. Kaplan-Meier curves will be estimated by cohort.

Table 7.5.2: 1 Censoring Rules for time to recurrence

| No. | Scenario | Relative Day of Event or Censoring | Outcome |
|-----|--|---|--------------------|
| 1 | A patient meets more than one recurrence rule | Earliest day of recurrence | Event (Recurrence) |
| 2 | A patient completed the treatment and follow-up without recurrence | Last day of follow-up | Censored |
| 3. | SAE after completion of three injection | Day of SAE | Censored |

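### The SAP has no rule for CSFT and BCVA values taken after standard-of-care treatment of the study eye, so any such values enter the cohort summaries unflagged, mainly at Weeks 16 to 24

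*SAP*

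**What the plan says.** **When SoC is allowed (Protocol 4.2.1.1).** For the single-dose part and MRD cohorts 1 and 2, "administration of local SoC treatment such as IVT or peribulbar injections, laser, or other surgical treatment is allowed in clinically significant worsening of the disease". No start time is given. In follow-up, "starting at Visit 5), SoC therapy is at the discretion of the investigator". For cohort 3, other study-eye treatment is barred "unless rescue criteria are met", or if judged medically appropriate from Visit 6 on. Protocol 6.2.2.2 keeps patients on the visit schedule regardless.

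**How CSFT and BCVA are analysed.** SAP 6.3 on intercurrent events: "This section is not applicable". SAP 7.5.2 plans "Descriptive statistics for absolute values as well as changes from baseline (percent changes and changes in CSFT and changes in BCVA (study eye"), by dose group/cohort and in total, with time profiles. CSFT uses the Full Analysis Set and BCVA the Treated Set. Neither set has an SoC condition (SAP 6.4). SAP 6.7 uses all available values, including unscheduled ones, and takes the one nearest the planned day. Protocol 7.5 has no rule that sets post-SoC values to missing.

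**Where SoC does count.** The Evaluable Responders' Set (ERS), used for the cohort 3 responder analysis at Week 16, leaves out anyone who has "received SoC or any prohibited medication through week 16". SAP 7.2 presents rescue medication separately, without a link to the efficacy tables.

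**The concern.** The trial is uncontrolled, so change from baseline is the main evidence on retinal thickness and acuity. A patient who worsens, receives anti-VEGF as SoC and then improves contributes the improved value to the cohort summary. A reader of the table cannot tell that this happened.

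The follow-up visits matter because Protocol 1.3 gives the 12 weeks without study injections a purpose: "to study the durability of the treatment effect" and to inform later injection intervals. Late profiles that mix BI 836880 with SoC answer that question poorly. The SoC rules also differ by cohort, so cohort profiles are not alike in this respect, and the total column pools them.

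**Working it through.** **1. The plan's own figures.** Protocol 7.7 assumes a normal percent CSFT decrease with SD 16. For N=15, the median is at least 20% when at least 8 of 15 values are, so P = P(Bin(15, p) ≥ 8) with p = 1 − Φ((20 − t)/16), where t is the true decrease. For N=10 the median was simulated.

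| N | True decrease t | Table 7.7: 1, P(observed ≥ 20%) | Recomputed |
|---|---|---|---|
| 10 | 13 / 19 / 25 | 11.9 / 43.3 / 80.1 | 11.9 / 43.3 / 80.0 |
| 15 | 13 / 19 / 25 | 8.6 / 42.2 / 83.7 | 8.5 / 42.2 / 83.7 |

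The table reproduces. It models one response distribution and makes no allowance for SoC.

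**2. Where post-SoC values can arise** (Protocol 4.2.1.1):

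| Period | Cohorts 1 and 2 | Cohort 3 |
|---|---|---|
| Before Visit 5 (Week 12) | SoC for worsening | rescue criteria only |
| Visit 5 up to Visit 6 (Week 16) | investigator's discretion | rescue criteria only |
| From Visit 6 | investigator's discretion | as medically appropriate |

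At Week 12 there are two routes.
- *Earlier SoC.* This is SoC for worsening in cohorts 1 and 2, or rescue in cohort 3. Of the three criteria in Protocol 5.2.2, the two that compare BCVA with baseline or with the best prior value can be met before Visit 5.
- *Value selection.* The Week 12 interval is days 72 to 99, planned day 85 (SAP Table 6.7: 1). The visit window of ±3 days allows Visit 5 on day 82, which is 3 days away. If SoC is given then, an unscheduled value on days 83 to 87 is at most 2 days away and replaces the pre-SoC value. If Visit 5 is missed, a value as late as day 99 can stand in.

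**3. An inconsistency at Week 16.** A cohort 3 patient rescued before Week 16 is removed from the responder analysis by the ERS definition. The same OCT stays, unmarked, in the Week 16 CSFT profile.

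**4. Size, under assumptions.** The documents give no number of SoC users (k) and no gain from SoC (s). Cohort sizes are 11, 4 and 12 (SAP 6.1). The mean moves by k·s/N. The median was simulated (SD 16, 1,000,000 repetitions), giving the gain to the patients with the smallest decreases, since worsening is what triggers SoC.

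| N | Assumption | Mean shift (points) | Median shift (points) |
|---|---|---|---|
| 11 | worst 1, s = 10 | 10/11 = 0.9 | 0.04 |
| 11 | worst 3, s = 10 | 30/11 = 2.7 | 1.0 |
| 11 | worst 3, s = 12 | 36/11 = 3.3 | 1.6 |
| 11 | worst 3, s = 20 | 60/11 = 5.5 | 4.5 |
| 4 | worst 1, s = 10 to 20 | 2.5 to 5.0 | 1.4 to 4.4 |

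For N=11 and a true decrease of 13%, the chance of observing a median of at least 20% is about 12% without SoC. It becomes about 14%, 16% and 32% when the worst three gain 10, 12 and 20 points. If the three were unrelated to response, s = 12 would give 26.2%.

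For BCVA, an assumed gain of 5 to 10 letters in one patient moves the mean by 1.25 to 2.5 letters (N=4), 0.45 to 0.91 (N=11) or 0.42 to 0.83 (N=12).

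**5. Would dropping post-SoC values solve it?** Removing the worst 3 of 11 raises the mean by 6.8 points and the median by 5.5. Under the same assumptions, that exceeds the shifts in step 4.

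**The case against.** **Week 12.** A reader might infer that the Week 12 results contain post-SoC values and are biased upward. The documents do not show this. Discretionary SoC in cohorts 1 and 2 starts at Visit 5 itself, so a scheduled Visit 5 value normally comes first, and cohort 3 needs rescue criteria until Visit 6. No SoC rate is reported. This stands, and only the two narrower routes in step 2 remain.

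**Durability.** A reader might infer that the plan leaves durability unprotected. It does not: time to recurrence is a secondary endpoint with Kaplan-Meier curves by cohort, and rescue on the stated criteria after the third injection is its event. That does not repair the CSFT and BCVA profiles. In cohorts 1 and 2, SoC given at discretion without those criteria is neither an event nor a censoring reason in SAP Table 7.5.2: 1.

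**Mean against median.** The planning benchmark of 25% is a median, and the percent-CSFT profiles show the median with minimum and maximum. The median resists one or two changed values, as step 4 shows. This stands for percent CSFT. The tables still give means, and the profiles of absolute CSFT and BCVA use means.

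**Traceability and choice of estimand.** Individual values and profiles are provided, so SoC use can be traced by hand in cohorts this small. Using all values is a defensible treatment-policy choice, and the ERS serves a different endpoint. Both points are fair, but the SAP never states that choice, and the result then describes BI 836880 plus SoC.

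**Visibility.** SAP 7.6.1 and Protocol 7.3.3 are not in the public text. The gap is shown for SAP 6.3, 6.7 and 7.5.2, the last of which governs these secondary endpoints.

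**Conclusion.** The gap is real and should be closed. If SoC is given to the study eye, the plan as written puts the later CSFT and BCVA values into the cohort summaries without a mark, and an uncontrolled reading would credit any SoC effect to BI 836880. The exposed results are chiefly the Week 16 to 24 profiles: after Visit 5 in cohorts 1 and 2, after Visit 6 in cohort 3. Week 12 is exposed less, through earlier SoC or through unscheduled or late values in the day 72 to 99 interval.

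The size cannot be derived from the documents. The illustration of 2.7 to 5.5 points on the mean and about 1.0 to 4.5 on the median rests on three assumptions: 3 of 11 patients receive SoC, they are the worst responders, and each gains 10 to 20 points. With one such patient gaining 10 points, the median hardly moves. The trial is descriptive with safety primary endpoints, so no error rate or formal decision is affected.

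**What to change.** These are changes to the analysis only. The treatment rules stay as they are.

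- In SAP 6.3, name first SoC or rescue treatment of the study eye as an intercurrent event for CSFT and BCVA.
- Keep the as-observed summary and label it treatment-policy.
- Report, by cohort, the number of patients with study-eye SoC before each visit.
- Mark post-SoC points in the individual profiles.
- In SAP 6.7, where a visit interval holds values from before and after SoC, select the last one before SoC.
- Add a supplementary summary that keeps the patients who worsened, for example by carrying the last pre-SoC value forward or counting SoC as failure. Protocol 7.5 plans no imputation of missing efficacy data, so list this as an addition in SAP 4.
- If a summary without post-SoC values is also shown, state beside it that it removes patients who worsened and can flatter the result.

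The cost is one flag built from concomitant-therapy data already collected, a few repeated tables and a paragraph in the SAP. The supplementary summary rests on an assumption of its own, which should be stated with it.

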6.4 SUBJECT SETS ANALYSED

Enrolled set (ES):

This subject set includes all patients who were enrolled in the study regardless of whether they were treated or not. The ES is used for the disposition table / listing and the disclosure tables for enrolment.

Section 7.3 of the CTP:

Treated Set (TS)

The TS will consist of all patients who were treated with at least one dose of BI 836880.

Full Analysis Set (FAS; only MRD part)

The FAS will consist of all patients who were treated with at least one dose of BI 836880 and have baseline and on-treatment CSFT measurements for the study eye in the time interval from drug administration to week 12. It will be used for the analysis of CSFT (change and percent change) only.

Evaluable Responders' Set (ERS, MRD cohort 3 only):

The ERS will consist of all patients who completed three doses of BI 836880 and have SD-OCT measurements at Week 16 (Visit 6) and haven't received SoC or any prohibited medication through week 16.

Patients with iPDs related to efficacy assessments that are expected to majorly affect the validity of assessment of efficacy at week 16 will be excluded from ERS. These include for

e.g., lack of compliance (including missed treatments, treatment misallocation and treatment/OCT assessment outside window), missing data, SoC or any prohibited medication, improper assessment at reading center and deviation from inclusion/exclusion criteria.

Any dropouts or withdrawals prior to completion of three doses of BI 836880 will be considered as a criterion of exclusion from ERS. In addition, any dropouts or withdrawals after completion of three doses of BI 836880 will also be excluded from ERS, unless SD-OCT measurements are available for that patient at Week 16.

Pharmacokinetic parameter analysis set (PKS):

This set includes all subjects in the treated set (TS)

- who received at least one dose of the test product BI 836880 and
- who provide at least one PK endpoint that was not excluded due to a protocol deviation relevant to the evaluation of PK or due to PK non-evaluability. Thus, a subject will be included in the PKS, even if he contributes only one PK parameter value for one period to the statistical assessment.

Descriptive and model-based analyses of PK parameters will be based on the PKS.

Table 6.4: 1 Subject sets analyzed

| Class of endpoint | ES | TS | FAS | ERS | PKS |
|---|----|----|-----|-----|-----|
| Primary endpoints | | X | | | |
| Analysis of CSFT (percent) change from baseline – MRD part only | | | X | | |
| Other secondary and further endpoints | | X | | | |
| Responder analysis | | | | X | |
| Safety parameter | | X | | | |
| Demographic/baseline parameter | | X | | | |
| Important protocol deviations | | X | | | |
| Disposition/Disclosure (enrolment) | X | | | | |
| PK, ADA and PD analysis | | | | | X |

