#### 6.2.2.2 Treatment period and end of trial visit MRD part

IVT injections must be carried out according to medical standards and applicable guidelines by a qualified physician experienced in administering IVT injections and will be done as part of Visit 2, Visit 3, and Visit 4 procedures after the other ophthalmologic assessments in the [Flow Charts II](#), [III](#), and [IV](#) have been performed (please see [Section 4.1.5](#) for details). An additional tonometry may be performed after IVT injection to monitor intraocular pressure. In the MRD part cohorts 2 and 3, additional safety assessments/visits will be carried out within a week after V2, V3, V4, respectively.

Patients must continue to be followed according to the visit schedule (unless they withdraw consent for further follow-up) in order to collect data at the end of the planned observation period. Unscheduled visits will be possible at the discretion of the investigator at any time for safety reason. The unscheduled visit may include any assessments considered necessary by the investigator. All unscheduled visits should be described and documented in the medical /source record. The investigator may decide to administer standard treatment for wAMD during the follow-up period (for MRD cohort 3 during/after Visit 6) as deemed medically appropriate.

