### Evaluable Responders' Set (ERS, MRD cohort 3 only)

The ERS will consist of all patients who completed three doses of BI 836880 and have SD-OCT measurements at Week 16 (Visit 6).

In the TSAP, the FAS and ERS definitions may be updated, and further analysis data sets may be defined.

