4. CHANGES IN THE PLANNED ANALYSIS OF THE STUDY

All analyses as planned in CTP will be performed and are described in more detail in this TSAP.

The baseline definition of CTP was clarified in TSAP:

In CTP Section 5.1 it is '*For the endpoints, baseline is defined as the value at Visit 2; if not measured at Visit 2 then baseline is the value at Visit 1*'. If an actual time is given in the data, it will be checked whether the measurement at visit 2 was done before or after trial drug administration. If it is done after administration, the measurement will not be used as a baseline measurement. The baseline definition was updated to 'The baseline value is defined as the last measurement before first administration of BI 836880 (= value at V2, in case no actual time is given in data)'.

The definition of responder in further endpoints was clarified in TSAP. In CTP section 2.2.2, one of the further endpoints in MRD part is "Responder (yes/no) defined as absence of intra-retinal or sub-retinal fluid (IRF/SRF) or resolution of SHRM/PED in the study eye at Week 16 (Visit 6, cohort 3 only)". This definition is modified as: "Responder (yes/no) defined as resolution of IRF and SRF or resolution of SHRM/PED in the study eye at Week 16 (Visit 6, cohort 3 only)". To avoid redundancy, endpoint "Absence (yes/no) of intra-retinal or sub-retinal fluid (IRF, SRF) in the study eye at Week 16 (Visit 6, cohort 3 only)" and "Resolution (yes/no) of subretinal hyper-reflective material/retinal pigment epithelial detachment (SHRM/PED) in the study eye at Week 16 (Visit 6, cohort 3 only)" could be removed.

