6.7 BASELINE, TIME WINDOWS AND CALCULATED VISITS

The baseline value is defined as the last measurement before first administration of BI 836880 (= value at V2, in case no actual time is given in data).

Section 5.1 of the CTP: *For the endpoints, baseline is defined as the value at Visit 2; if not measured at Visit 2 then baseline is the value at Visit 1.*

The acceptable time windows for visits are given in the CTP Flow Chart.

Adherence to time windows will be checked via the consistency check listings at the MQRM/RPM/DBLM.

To utilize all available data, including values collected between protocol-specified visit windows and unscheduled visits, time intervals will be defined for analysis of efficacy data. If multiple values are recorded within a visit interval, the value collected closest to the planned visit date will be included in analyses of efficacy endpoints (CSFT, BCVA, and responder analysis) and IOP.

Unscheduled measurements of laboratory data and vital signs data will be assumed to be repeat measurements of the most recent scheduled measurement (e.g. for follow-up or confirmation of a particular value). Therefore, unscheduled measurements will be assigned to the planned time point of the previous scheduled measurement.

Table 6.7: 1 Visit intervals for efficacy endpoints (CSFT, BCVA, responder analysis) and IOP

| Visit | Planned day | Interval Definition | | Visit description |
|--------------|--------------------|----------------------------|----------------------|--------------------------|
| | | From (day) | To (day) | |
| 1 | -28 to -3 | NA | -1 | Screening |
| 2 | 1 | 1 | 1 | Baseline |
| 3 | 29 | 2 | 43 | Week 4 |
| 4 | 57 | 44 | 71 | Week 8 |
| 5 | 85 | 72 | 99 | Week 12 |
| 6 | 113 | 100 | 127 | Week 16 |
| 7 | 141 | 128 | 155 | Week 20 |
| 8 | 169 | 156 | Last assessment date | Week 24 |

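### The SAP's Evaluable Responders' Set has no cut-off at the Week 16 scan, so read literally it drops cohort 3 patients given permitted standard of care at Visit 6 after a valid scan

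*SAP*

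**What the plan says.** **ERS in the protocol.** Section 7.3 asks for three doses and a Week 16 scan and sets no SoC condition: "The ERS will consist of all patients who completed three doses of BI 836880 and have SD-OCT measurements at Week 16 (Visit 6" (the sentence ends there). It also lets the TSAP update this definition.

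**ERS in the SAP.** Section 6.4 adds that patients "haven't received SoC or any prohibited medication through week 16". The addition sits in text introduced as coming from protocol 7.3, and SAP section 4, which lists changes to the planned analysis, does not mention it. On later dropouts, the same section says that they "will also be excluded from ERS, unless SD-OCT measurements are available for that patient at Week 16".

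**SoC in cohort 3.** Protocol 4.2.1.1 bars other study-eye treatment unless the rescue criteria are met, "or as deemed medically appropriate during/after Visit 6". Protocol 6.2.2.2 repeats the permission: "for MRD cohort 3 during/after Visit 6) as deemed medically appropriate".

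**Timing and endpoint.** The row for Visit 6 in SAP Table 6.7: 1 reads "6 | 113 | 100 | 127 | Week 16" (visit, planned day, interval start, interval end, label). SAP section 4 gives the endpoint as "Responder (yes/no) defined as resolution of IRF and SRF or resolution of SHRM/PED in the study eye at Week 16". SAP Table 6.4: 1 assigns it to the ERS alone: "Responder analysis | | | | X".

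**The concern.** SoC becomes available without the rescue criteria at the same visit at which the endpoint is measured. A patient who attends Visit 6, is scanned, and is then treated has followed the protocol, and the scan carries no SoC effect. The SAP wording does not separate this patient from one treated before the scan.

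Two things follow. First, a valid endpoint is discarded because of something that happened after it was recorded. If that later decision is related to what the scan showed, the remaining patients are a selected group. Second, two programmers could read the Week 16 limit differently and derive different sets from the same data. With about 12 patients in the cohort, each exclusion moves the rate visibly.

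**Working it through.** The documents give no responder rate, ERS size or formal sample-size calculation for cohort 3, so there is no figure of the plan's own to reproduce. The check has three steps.

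**1. Apply each rule to one patient.** The patient has three doses, a Visit 6 SD-OCT, and permitted SoC later the same day.

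- Protocol 7.3: three doses and a Week 16 scan, so the patient is **in**.
- SAP 6.4, read literally: SoC was received at Week 16, so the patient is **out**.
- SAP 6.4, with Week 16 read as the assessment itself: no SoC preceded the scan, so the patient is **in**.

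The documents do not state the order of scan and SoC at Visit 6. Study-drug injections at Visits 2 to 4 follow the ophthalmic assessments (protocol 6.2.2.2), so a scan before SoC is the natural assumption.

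**2. Is the case foreseeable?** The third dose is planned for Day 57 and Visit 6 for Day 113. The gap is 113 − 57 = 56 days. Inclusion criterion 18 requires earlier SoC intervals of 28 to 56 days, so Visit 6 falls at the upper end of the interval these patients were used to. SoC at Visit 6 could be common. The documents do not say how common.

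**3. Effect on the rate.** Let N patients have valid Week 16 scans, R of them responders. The literal rule removes k patients, r of them responders.

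- Rate with all valid scans: R/N
- Rate under the literal rule: (R − r)/(N − k)
- The second exceeds the first when N(R − r) > R(N − k), that is, when **r/k < R/N**

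So the rate rises only if responders are rarer among the removed patients than overall. N = 12 is the planned cohort size. R, k and r are assumptions. With R = 4 the full rate is 4/12 = 33.3%:

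| k removed | r responders among them | Literal ERS rate | Difference (points) |
|---|---|---|---|
| 1 | 0 | 4/11 = 36.4% | +3.0 |
| 2 | 0 | 4/10 = 40.0% | +6.7 |
| 3 | 0 | 4/9 = 44.4% | +11.1 |
| 4 | 0 | 4/8 = 50.0% | +16.7 |
| 3 | 1 | 3/9 = 33.3% | 0.0 |
| 2 | 1 | 3/10 = 30.0% | −3.3 |

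With R = 6 the full rate is 50.0%. Removing 2, 3 or 4 non-responders gives 6/10 = 60.0%, 6/9 = 66.7% or 6/8 = 75.0%. Removing 2 of whom 1 is a responder gives 5/10 = 50.0%.

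**The case against.** The best reply is that the wording can be taken to mean up to the Week 16 assessment. The next paragraph of SAP 6.4 aims at deviations that would undermine the Week 16 efficacy assessment, and SoC given after the scan cannot do that. SoC at Visit 6 is permitted, so it is not prohibited medication under code D2 of SAP Table 6.2: 1 either. This shows what the authors probably intended. It does not remove the problem, because the rule as written contains no such limit and the favourable reading has to be supplied by whoever programs it.

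A reader might infer that the lost scans come mostly from eyes that are still active and that the responder rate is therefore inflated. The documents do not support that. The permission rests on medical judgement, not on activity. Visit 6 comes 56 days after the third dose, so some eyes may be re-treated on schedule without activity. A patient can also be a responder through SHRM/PED alone and still be treated. This part of the objection stands, and it is why the direction is stated as probable only.

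A reader might also extend the exclusion to SoC given up to Day 127. Table 6.7: 1 assigns measurements to visits. Nothing there says that it defines the period for the SoC exclusion, so that is only one possible reading.

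Finally, SAP 7.6.1 and protocol 7.3.3 are not in the public text. The description of Global Amendment 7 records that 7.3.3 bases the responder analysis on the TS and/or the ERS. A supporting analysis in the Treated Set therefore cannot be ruled out, although Table 6.4: 1 shows none.

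**Conclusion.** The point holds as a defect in a stated rule. Followed literally, SAP 6.4 removes protocol-compliant patients whose Week 16 endpoint was observed before any SoC, and whom the protocol's ERS keeps. Because the exclusion depends on a decision taken after the assessment, it can bias the reported rate.

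Upward bias is the more likely direction, since treatment by medical judgement would tend to go to eyes that have not responded. That is an inference. The size depends on how many patients receive SoC at Visit 6 and on their response status, and the documents give neither. In the illustrations with 4 responders among 12, the difference runs from −3.3 to +16.7 points, and it is zero when the removed patients respond at the overall rate.

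Severity is minor. This is a descriptive further endpoint in an uncontrolled cohort of about 12. No hypothesis is tested, the primary and secondary endpoints are unaffected, and individual values will be listed. Patients who receive SoC before the Week 16 scan are a separate matter, which this point does not address.

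**What to change.** In SAP 6.4, replace the Week 16 limit so that the ERS requires no SoC in the study eye, and no prohibited medication, before the SD-OCT used as the Week 16 (Visit 6) assessment. Patients given SoC only after that scan then stay in the ERS with their observed result. The mention of SoC among the example deviations in the next paragraph should follow the same cut-off.

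State how same-day SoC is handled, for example as given after the scan unless recorded times show otherwise.

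Keep the rule in SAP 6.7 that takes the value closest to the planned visit date. Choosing instead the closest scan before SoC would depart from that rule and could promote an early unscheduled scan to Week 16.

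The cost is one sentence in the SAP and one date comparison in the ERS derivation. The reported responder rate may become less favourable.
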